6.2. Risks associated with study procedures

6.2.1. Opioid withdrawal procedure

Opioid withdrawal symptoms can occur during dosage reduction, specifically for rapid dosage reduction of short-acting, high-dose opioids. In contrast, the protocol here involves gradual dosage reduction (approximately 25% per week) of primarily long-acting (e.g. methadone, oxycodone), and exclusively low-dose (below 60 MME) opioids. Therefore, we expect a low risk of opioid withdrawal symptoms. However, it is possible that one or more symptoms that are associated with opioid withdrawal [11] may occur, such as the following: agitation, restlessness, and anxiety, depression, insomnia, yawning, increased tearing or watery eyes, runny nose, sweating, shivering, trembling, or goosebumps, muscle aches or joint pain, nausea or vomiting, abdominal cramps, diarrhea. Subjects will undergo a weekly investigator assessment and subjects with clinically significant withdrawal symptoms will be excluded from further participation. Moreover, subjects with intolerable withdrawal symptoms will have the option to discontinue participation at any time and revert to their original opioid dosage.

7. Adverse Events

Anticipated observations (e.g. common treatment effects) and adverse events occurring during the study will be recorded. Descriptions of anticipated observations and AEs will include the date of onset, the date it ended, the severity, the relationship to study device, and the outcome. All reported AEs will be summarized by the number of subjects reporting AEs, system organ class (where applicable), severity, seriousness, and relationship to study device.

The study Investigator and Coordinator will evaluate, characterize and record in the Case Report Form (CRF) all adverse events (AEs) occurring in all subjects from the time of enrollment to study exit (or premature withdrawal). Adverse events unresolved at study exit will be followed by the Investigator until resolution occurs or at least 60 days after the subject's participation in the study is complete. AEs may be reported spontaneously by the subject or detected by the Investigator or Coordinator. AEs should be evaluated for diagnoses not just symptoms (i.e., "angina", not "chest pain").

CONFIDENTIAL

All information contained in this document is confidential and is the sole property of Noctrix Health, Inc.
Any reproduction in part or whole without the written permission of Noctrix Health, Inc. is prohibited.

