13.2 Run-in and Assessment periods

[figure not shown]
Each Phase involves a 1-2 week run-in period followed by a 1-week assessment period. Assessment periods are primarily designed for endpoint evaluation. Run-in periods are designed for two reasons: (i) to provide a run-in phase to optimize instructions for NPNS device self-administration (e.g. timing and intensity) and (ii) so that any opioid withdrawal symptoms unrelated to the RLS condition resolve prior to the assessment period. Each run-in period will last a minimum of 1-week and a maximum of 2-weeks.

The investigator is permitted to adjust the instructed schedule of opioid medication and/or NPNS usage during a Step-Down based on clinical evaluation of response to opioid treatment and NPNS.

CONFIDENTIAL

All information contained in this document is confidential and is the sole property of Noctrix Health, Inc.
Any reproduction in part or whole without the written permission of Noctrix Health, Inc. is prohibited.

Figure 1. Flowchart of Run-in and Assessment periods for Phases 1 & 2

Additionally:

[figure not shown]
- If clinically significant opioid withdrawal symptoms unrelated to RLS become intolerable during the run-in period for a given Phase, participation will be discontinued and data from the subject will not count towards the efficacy endpoints for that Phase.
- If opioid withdrawal symptoms related to RLS become intolerable at any point during a run-in period, participation will be discontinued and the subject will count towards the efficacy endpoints for that Phase.
- The investigator may decide that participation should be discontinued at any time if there are excessive opioid withdrawal symptoms, even if those symptoms are tolerable.
- If opioid withdrawal symptoms become intolerable mid-week during a run-in period, participation will be discontinued.
- In all cases, efficacy outcome measures CGI-I and IRLS will be assessed at study exit but will not be included in analysis of the efficacy endpoints unless opioid withdrawal symptoms related to RLS was the primary reason for discontinuation.
- The Extension Phase is optional and requires approval by both the investigator and the participant. The structure of this phase is similar phases 1 and 2.

CONFIDENTIAL

All information contained in this document is confidential and is the sole property of Noctrix Health, Inc.
 Any reproduction in part or whole without the written permission of Noctrix Health, Inc. is prohibited.

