16.5. Baseline Assessments

The participant completes an IRLS questionnaire describing their symptoms and experiences over the past week and a demographic/characterization assessment including questions about their history of RLS symptoms and medication(s).

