16.10. Study Exit

Study exit will typically occur either at the end of either Phase 1 (Eval #6), Phase 2 (Eval #11), or Phase 3 (Eval #16), based on the guidelines provided in Section 13. Study exit may occur earlier if the opioid reduction in a phase is not tolerable; if so, a final clinic visit will be scheduled to conduct the final assessments.

When the final follow-up visit is complete, the Investigator/coordinator will complete the study exit CRF. Adverse events unresolved at study exit will be followed by the Investigator until resolution occurs or at least 60 days after the subject's participation in the study is complete.

CONFIDENTIAL

All information contained in this document is confidential and is the sole property of Noctrix Health, Inc. Any reproduction in part or whole without the written permission of Noctrix Health, Inc. is prohibited.

 NOCTRIX HEALTH	Clinical Trial Investigational Plan, Protocol CT-03 (Opioid Reduction Study)	Document #: CT-2 (Previously CT-03) Rev: 4.0 (Superseded Rev C) CC#: 720 (Previously DCO #138) Effective: 09/24/2021
---	---	---

Both IRLS and CGI-I will be administered at study exit.

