17.1. Efficacy

In the absence of an adjunctive treatment, a reduction in opioid dose will cause an increase in RLS symptoms. The efficacy of NPNS will be assessed by its capacity to prevent this increase in RLS symptoms. Subjects who discontinue due to nonspecific opioid withdrawal symptoms will not be included in the efficacy analysis but will be considered in the safety analysis. Efficacy endpoints will be calculated during the Assessment period except in cases of dropout during the run-in period(s); Section 13.2 describes how efficacy endpoints will be calculated in cases of dropout during the run-in period(s).

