17.1.3. Efficacy Analysis

Endpoints 1 and 2 are calculated with the following formula, respectively for Phases 1 and 2:

$100\% * ((X - Y) / (N - M))$, where

- N = Number of subjects who entered the Run-in period for the Phase.
- M = Number of subjects excluded during Run-in period due to non-RLS opioid withdrawal symptoms.
- Y = Number of subjects excluded during Run-in period primarily due to intolerable RLS symptoms.
- X = Number of subjects who complete Assessment period with no clinically significant worsening in Clinical Global Impression-Improvement scale (CGI-I) relative to Baseline, where a clinically significant worsening is defined by a score of 6 (Much worse) or 7 (Very much worse).

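### Sections 13.2 and 17.1.3 give competing rules for subjects who leave during run-in because of RLS symptoms, and the timing of their exit ratings is not fixed

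*Combined protocol and SAP*

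**What the plan says.** **Dropout rule.** Section 17.1 bases the efficacy endpoints on the Assessment period. For run-in dropouts it adds: "Section 13.2 describes how efficacy endpoints will be calculated in cases of dropout during the run-in period(s". Section 13.2 says two things about a subject who stops in run-in because of RLS-related symptoms. First, "participation will be discontinued and the subject will count towards the efficacy endpoints for that Phase". Second, the CGI-I and IRLS taken at study exit "will not be included in analysis of the efficacy endpoints unless opioid withdrawal symptoms related to RLS was the primary reason for discontinuation". It does not say whether such a subject counts as a failure or according to the exit score.

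**Formula.** Section 17.1.1 defines success for Endpoints 1 and 2 as a CGI-I of 5 or less. Section 17.1.3 calculates both as 100% * (X - Y)/(N - M):
- N is everyone who entered the run-in for the Phase.
- M is those lost in run-in to non-RLS withdrawal symptoms.
- Y is the "Number of subjects excluded during Run-in period primarily due to intolerable RLS symptoms".
- X is the "Number of subjects who complete Assessment period with no clinically significant worsening in Clinical Global Impression-Improvement scale (CGI-I) relative to Baseline", where worsening means a score of 6 or 7.

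Section 17.1.3 says nothing about Endpoints 3 to 5. Under Section 17.1.5 the study passes if Endpoint 1 exceeds 50 percent. The Synopsis plans 20-40 subjects in the primary study.

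**Exit ratings.** After an early stop, Section 16.10 says "a final clinic visit will be scheduled to conduct the final assessments". Section 6.2.1 lets subjects with intolerable withdrawal symptoms "discontinue participation at any time and revert to their original opioid dosage". Section 16.5 describes the baseline IRLS as "an IRLS questionnaire describing their symptoms and experiences over the past week".

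**The concern.** An analyst cannot follow both sections for Endpoints 1 and 2. Section 13.2, to which Section 17.1 defers, admits the exit CGI-I of an RLS dropout; set beside the endpoint definition, a score of 5 or less could then make that subject a success. Section 17.1.3 has no place for an exit CGI-I, and it counts the same subject against the result twice: once by leaving the subject in N but out of X, and again by subtracting Y. The primary criterion is a bare point estimate in a small study, so a few subjects can decide it.

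A second, separate matter concerns what the exit ratings measure. In Phases 1 and 2, Table 5A schedules the CGI-I only at Evals 6 and 11, so a run-in dropout's exit CGI-I is the only one for that Phase. No section says whether it is taken before or after any return to the original opioid dose. If it came after, exit IRLS in Endpoints 3 and 4, and exit CGI-I in Endpoint 5, would partly describe a restored dose.

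**Working it through.** The plan gives no assumed success rate, dropout rate or sample-size derivation, so there is no planned figure to reproduce. The formula, the 50% threshold and the 20-40 range come from the documents. All counts and rates below are assumptions.

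**Three rules**, where k of the Y dropouts have an exit CGI-I of 5 or less:
- A, Section 17.1.3 as written: (X - Y)/(N - M)
- B, each dropout counted once as a non-success: X/(N - M)
- C, exit CGI-I used, as 13.2 can be read: (X + k)/(N - M)

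**One example.** N = 20, M = 0, X = 10, Y = 4, k = 2:
- A: (10 - 4)/20 = 30%, fail
- B: 10/20 = 50%, fail, since the criterion is above 50%
- C: (10 + 2)/20 = 60%, pass

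**Rule A can also turn a pass into a fail.** With N = 20, M = 0, X = 12, Y = 3, rule B gives 12/20 = 60% (pass) and rule A gives (12 - 3)/20 = 45% (fail).

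**Smallest X that passes (M = 0):**

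| N | Y | A | B | C, all Y rated 5 or less |
|---|---|---|---|---|
| 20 | 3 | 14 | 11 | 8 |
| 40 | 6 | 27 | 21 | 15 |

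Under A, even if every other subject succeeds, Y = 5 of 20 gives (15 - 5)/20 = 50% and Y = 10 of 40 gives (30 - 10)/40 = 50%. A pass is therefore impossible from those counts upward. The result can be negative: N = 20, X = 4, Y = 6 gives -2/20 = -10%, which cannot be a percentage of subjects.

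**Chance of passing**, if 45% of entrants complete the Assessment period as successes and 15% leave in run-in for RLS (M = 0; binomial for B, 200,000 simulated trials for A and C):

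| N | A | B | C, 25% / 50% / 100% of dropouts rated 5 or less |
|---|---|---|---|
| 20 | 8% | 25% | 37% / 50% / 76% |
| 40 | 3% | 21% | 38% / 57% / 87% |

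**Timing.** Section 16.10 places the final assessments at a visit scheduled after an early stop, with no time limit. Section 6.2.1 allows the original dose to be resumed on discontinuing. No section fixes the order. The rule in Section 17.1.2 that the dose actually taken is used covers Assessment periods only, so it does not reach a run-in exit visit. If each of Y dropouts had an exit IRLS d points below the reduced-dose value, the mean over n subjects would fall by Y * d/n; with Y = 4 and n = 20 that is 0.2 points per point of d. The documents give no basis for d.

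**The case against.** The strongest reply is that 17.1.3 is the only place where Endpoints 1 and 2 are computed, and that its X is confined to subjects who complete the Assessment period. On that view a run-in dropout can never be a success. The statement in 13.2 that such subjects count is satisfied by their place in N and Y, and the exit ratings serve Endpoints 3 to 5. This is a coherent reading, and 13.2 never says that an exit score of 5 or less is a success. It is not the only reading, however: 17.1 names 13.2 as the dropout rule, and 13.2 admits the exit CGI-I without limiting it to certain endpoints. Nor does it remove the double subtraction.

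A reader might infer that the exit ratings turn failures into successes and that every effect here favours NPNS. The documents do not support that. As written, 17.1.3 penalises NPNS; an upward shift in Endpoints 1 and 2 needs 13.2 to override the formula. For IRLS there is no clash at all, because 17.1.3 does not address it.

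A reader might also infer that exit ratings are made on a restored dose. The text leaves this open and does not prescribe it. Section 17.1.1 ties Endpoints 1 to 4 to the Phase with the stated dose reduction. The withdrawal question in Section 17.3 speaks of wanting to return to the original dose, which suggests that at least that form comes first. A prompt exit IRLS would still cover mostly reduced-dose days. The one-week recall is stated for baseline and is assumed to apply at exit.

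The study is titled exploratory, Endpoints 3 and 4 carry no success criterion, and Figure 1 (the run-in flowchart) could not be read, so it is not known whether it adds a rule.

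**Conclusion.** The point holds as an unresolved conflict in the scoring of the primary endpoint. For the same data, the text supports a score of -1 for an RLS run-in dropout (17.1.3 as written) and, on one reading of 13.2, +1 if the exit CGI-I is 5 or less. In the 20-subject example the result is 30%, 50% or 60% according to the rule. The counts are assumed; that the rules differ is not. The direction is mixed: against NPNS if 17.1.3 governs, possibly in its favour if 13.2 does.

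The timing gap is narrower. Exit IRLS enters Endpoints 3 and 4, and exit CGI-I may enter Endpoint 5, with nothing to show which dose the rating reflects. Whether this happens, and how much it matters, cannot be judged from the documents.

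**What to change.** - **Endpoints 1 and 2.** State in both 13.2 and 17.1.3 that a run-in discontinuation primarily for RLS is a non-success, counted once, whatever the exit CGI-I: 100% * X/(N - M).
- **Endpoint 5.** State that an exit CGI-I from such a dropout does not credit that Phase's dose reduction.
- **Exit form.** Record the date of the exit rating and the opioid dose taken over the IRLS recall week.
- **Endpoints 3 and 4.** Flag exit IRLS values whose recall week includes a restored dose, and report results with and without them. Use the last IRLS on the reduced dose (Eval 3 or 5, 8 or 10), where one exists, as a sensitivity analysis only. The first run-in IRLS is due at day 7, so earlier dropouts have none, and an earlier value may predate the worsening that led to exit.
- **Consistency.** Reconcile Sections 6.2.1, 13.2, 16.10 and 17.1.3. This concerns analysis and recording only; no dose or clinical rule is proposed.

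The cost is a few sentences, one or two fields on the exit form and a little extra analysis, with no added visit. Endpoint 1 may move up or down, depending on which of the present rules would have been applied.

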16.1. Recruitment

Recruitment will initially focus on patients whose opioid medications are managed by a Study Investigator at the time of study entry. Recruitment may be expanded if additional subjects are needed to meet the enrollment target. Subject eligibility will be determined based on the inclusion and exclusion criteria detailed above. Eligible applicants who chose to participate and sign the informed consent form will be enrolled in the study. A pre-screening call may be completed prior to the first in-person visit (and thus prior to consent) to exclude ineligible applicants prior to the in-person visit. Patients not referred by the investigator may be contacted by the investigator to establish whether they meet criteria for clinical RLS; applicants who do not meet clinical criteria for a diagnosis will be excluded from remaining parts of the study. Eligibility is contingent on scheduling constraints, such as research facility and research staff availability.

16.2. Informed consent Process

All participants must be provided a consent form describing the study with sufficient information for participants to make an informed decision regarding their participation. Participants must sign the IRB approved informed consent prior to participation in any study specific procedure, with the exception of pre-screening. The participant must receive a paper or electronic copy of the signed and dated consent document. The signed copy of the consent document must be retained in the study binder in paper or electronic format. The schedule of visits and procedures is provided in Table 2.

16.3. Screening

Potential participants will be screened for eligibility based on the criteria in Section 4 above. A subject who is eligible and signs the study consent will be considered a study subject, and will be assigned a

CONFIDENTIAL

All information contained in this document is confidential and is the sole property of Noctrix Health, Inc.
Any reproduction in part or whole without the written permission of Noctrix Health, Inc. is prohibited.

 NOCTRIX HEALTH	Clinical Trial Investigational Plan, Protocol CT-03 (Opioid Reduction Study)	Document #: CT-2 (Previously CT-03) Rev: 4.0 (Superseded Rev C) CC#: 720 (Previously DCO #138) Effective: 09/24/2021
---	---	---

study ID number, will be considered enrolled and will count towards the study's sample size. A subject who withdraws or is removed from the study prior to receiving any study treatment will not count towards the study's sample size.

16.4. Pilot phase

Up to 10 subjects may be enrolled in a pilot phase. For each site, subjects enrolled in the pilot phase will precede subjects enrolled in the primary study. Subjects enrolled in the pilot phase will be specified at the time of enrollment such that their data will not be included in the analysis.

16.5. Baseline Assessments

The participant completes an IRLS questionnaire describing their symptoms and experiences over the past week and a demographic/characterization assessment including questions about their history of RLS symptoms and medication(s).

16.6. Device calibration and training

During the baseline (Eval #1) visit, the devices are calibrated for the subject and the thresholds are programmed into the devices. The calibration process is designed to identify the maximally effective settings that are comfortable for each subject. The calibration process is also used to evaluate Exclusion Criterion #10. Therefore, subjects may be excluded immediately following calibration and prior to training and study enrollment. The sponsor may administer the calibration and/or assist in administering the calibration.

Following calibration, subjects are trained on proper usage of the device, including positioning of the electrodes on their legs. Instrument(s) designed for marking the human skin (body-marking pen or temporary tattoo) may be employed to mark the locations of electrode placement.

16.7. Study Treatment Description

Study subjects are instructed to self-administer treatment for at least 30 minutes on each night that they experience RLS symptoms. Study subjects may self-administer up to four 30-min sessions per day, as needed based on RLS symptoms. The instructions for timing of these "as needed" doses will be determined at the discretion of the investigator and research staff, based on the RLS symptoms experienced by the subject.

CONFIDENTIAL

 NOCTRIX HEALTH	Clinical Trial Investigational Plan, Protocol CT-03 (Opioid Reduction Study)	Document #: CT-2 (Previously CT-03) Rev: 4.0 (Superseded Rev C) CC#: 720 (Previously DCO #138) Effective: 09/24/2021
---	---	---

16.8. Leg movement data collection

The NTX Neuromodulation System may have the capability to collect data on leg movements, such as by using accelerometers and/or gyroscope sensors, while the participant is wearing the devices. These data may be collected during this study and used for subsequent algorithm development.

16.9. Evaluation and study assessment schedule

The following evaluation calls and/or visits are scheduled, as outlined in Table 5 below:

Phase 1

- Evaluation 1: Enrollment, including consent, screening, device calibration, and training on device usage.
- Evaluation 2: (3-days after Eval. #1) Phone follow-up to assess NPNS use, medication use and opioid withdrawal tolerability.
- Evaluation 3: (7-days after Eval. #1) Phone follow-up to assess RLS severity, NPNS usage, and opioid withdrawal tolerability.
- Evaluation 4: (10-days after Eval #1) *Optional Evaluation, if additional time for adjusting to opioid reduction is needed.* Phone follow-up to assess NPNS usage, medication use, and opioid withdrawal tolerability,
- Evaluation 5: (14-days after Eval #1) *Optional Evaluation, if additional time for adjusting to opioid reduction is needed.* Phone follow-up to assess RLS severity, NPNS usage, and opioid withdrawal tolerability.
- Evaluation 6 (**Assessment period**): (7-days after last Eval. (3, 4 or 5)). Phone or Office follow-up to assess RLS severity (including CGI-I), NPNS usage, and opioid withdrawal tolerability. Second opioid reduction occurs, and Phase 2 of the study begins. If subject was unable to tolerate opioid withdrawal symptoms complete study exit assessments and close-out participation for the subject.

CONFIDENTIAL

All information contained in this document is confidential and is the sole property of Noctrix Health, Inc.

Any reproduction in part or whole without the written permission of Noctrix Health, Inc. is prohibited.

 NOCTRIX HEALTH	Clinical Trial Investigational Plan, Protocol CT-03 (Opioid Reduction Study)	Document #: CT-2 (Previously CT-03) Rev: 4.0 (Superseded Rev C) CC#: 720 (Previously DCO #138) Effective: 09/24/2021
---	---	---

Phase 2

- Evaluation 7: (3-days after Eval. #6) Phone follow-up to assess NPNS use, medication use and opioid withdrawal tolerability.
- Evaluation 8: (7-days after Eval. #6) Phone follow-up to assess RLS severity, NPNS usage, and opioid withdrawal tolerability.
- Evaluation 9: (10-days after Eval #6) *Optional Evaluation, if additional time for adjusting to opioid reduction is needed.* Phone follow-up to assess NPNS usage, medication use, and opioid withdrawal tolerability,
- Evaluation 10: (14-days after Eval #6) *Optional Evaluation, if additional time for adjusting to opioid reduction is needed.* Phone follow-up to assess RLS severity, NPNS usage, and opioid withdrawal tolerability.
- Evaluation 11 (**Assessment period**): (7-days after last Eval. (8, 9 or 10)). Office follow-up to assess RLS severity (including CGI-I), NPNS usage, and opioid withdrawal tolerability. Third opioid reduction occurs, and extension Phase 3 of the study begins if subject chooses to participate. If subject chooses not to continue with the extension Phase 3, complete study exit assessments and close-out participation for the subject.

Optional Extension

- Evaluation 12: (3-days after Eval. #11) Phone follow-up to assess NPNS use, medication use and opioid withdrawal tolerability.
- Evaluation 13: (7-days after Eval. #11) Phone follow-up to assess RLS severity, NPNS usage, and opioid withdrawal tolerability.
- Evaluation 14: (10-days after Eval #11) *Optional Evaluation, if additional time for adjusting to opioid reduction is needed.* Phone follow-up to assess NPNS usage, medication use, and opioid withdrawal tolerability,
- Evaluation 15: (14-days after Eval #11) *Optional Evaluation, if additional time for adjusting to opioid reduction is needed.* Phone follow-up to assess RLS severity, NPNS usage, and opioid withdrawal tolerability.

CONFIDENTIAL

 NOCTRIX HEALTH	Clinical Trial Investigational Plan, Protocol CT-03 (Opioid Reduction Study)	Document #: CT-2 (Previously CT-03) Rev: 4.0 (Superseded Rev C) CC#: 720 (Previously DCO #138) Effective: 09/24/2021
---	---	---

- Evaluation 16 (**Assessment period**): (7-days after last Eval. (13, 14 or 15)). Office follow-up to assess RLS severity (including CGI-I), NPNS usage, and opioid withdrawal tolerability. Complete study exit assessments and close-out participation for the subject.

Evaluations 1, 6, 11 and 16 are intended to be in-person and all other Evaluations are designed to be remote interactions (calls or video calls). Evaluations 1, 6, 11 and 16 may be replaced by remote interactions to the extent needed to reduce risk to participants and to the extent that technology allows for remote interactions. The proposed follow-up timelines are estimates, and they can be flexible as needed, within a +/- window of two days for each evaluation.

The schedule of each subjective study-related assessment, including endpoints, are shown in Table 5A below. Participants in the Extension Phase will complete an additional schedule of assessments as illustrated in Table 5B, which follow a similar structure to the assessments in Phase 2.

In addition to these assessments, the devices automatically log quantitative compliance, usage data, and leg movement data throughout the duration of the study.

The following are completed by subject: IRLS, Daily questionnaire, Medication use assessment, Step-down assessment questionnaire.

The following are administered and completed by the investigator or designee: Screen for inclusion/exclusion, Informed consent, Study entry questionnaire, CGI-I, Opioid-related symptom assessment, AE assessment.

CONFIDENTIAL

All information contained in this document is confidential and is the sole property of Noctrix Health, Inc.
 Any reproduction in part or whole without the written permission of Noctrix Health, Inc. is prohibited.

 NOCTRIX HEALTH	Clinical Trial					Document #: CT-2 (Previously CT-03) Rev: 4.0 (Superseded Rev C) CC#: 720 (Previously DCO #138) Effective: 09/24/2021				
	Investigational Plan, Protocol CT-03 (Opioid Reduction Study)									

Table 5A. Schedule of Assessments

	Baseline		Opioid Reduction Phase 1				Opioid Reduction Phase 2				Exit or Extension	
			Acclimate to Opioid Reduction (7-14 days)				7 days from last Eval (3, 4, or 5)	Acclimate to Opioid Reduction (7-14 days)				
	Pre-screening	Eval. #1 (clinic visit)	Eval. #2 (call) 3-days	Eval #3 (call) 7-days	Eval. #4 (call)* 10-days	Eval #5 (call)* 14-days		Eval. #6 (call or visit) End of Phase 1/ Start of Phase 2	Eval. #7 (call) 3-days	Eval #8 (call) 7-days	Eval. #9 (call)* 10-days	Eval #10 (call)* 14-days
Pre-screen inclusion/exclusion	X											
Screen inclusion/exclusion		X										
Informed consent		X										
Study entry questionnaire		X										
NPNS calibration & IFU training		X										
Dispense NPNS Device		X										
Calculate baseline opioid dose		X										
Incremental Opioid Dose Reduction		X						X				O
Review Daily Questionnaire			X	X	O	O	X	X	X	O	O	X
CGI-I							X					X
IRLS		X		X		O	X		X		O	X
Medication use assessment			X	X	O	O	X	X	X	O	O	X
Opioid withdrawal assessment		X		X	O	O	X	X	X	O	O	X
AE assessment				X		O	X		X		O	X
Step-down assessment questionnaire							X					X

*(O) = Optional, if additional time for adjusting to opioid reduction is needed.

Table 5B. Extension Phase Schedule of Assessments

	Opioid Reduction Phase 3 (Optional)				Study Exit	
	Acclimate to Opioid Reduction (7-14 days)				7 days from last Eval (13, 14 or 15)	
	Eval. #12 (call) 3-days	Eval #13 (call) 7-days	Eval. #14 (call)* 10-days	Eval #15 (call)* 14-days	Eval. #16 (clinic visit) End of Phase 2/ Start of Phase 3	
Review Daily Questionnaire	X	X	O	O		
CGI-I					X	
IRLS		X		O	X	
Medication use assessment	X	X	O	O	X	
Opioid withdrawal assessment	X	X	O	O	X	
AE assessment		X		O	X	
Step-down assessment questionnaire					X	

*(O) = Optional, if additional time for adjusting to opioid reduction is needed.

